During the OL period, in addition to the TB screening described above, laboratory tests (hematologic and chemical analysis, including hs-CRP) will be performed during study visits at Weeks 12, 16, 20, and 26/Premature Discontinuation, and urinalysis will be performed at Weeks 12, 20, and 26/Premature Discontinuation.

AEs will be collected during the study and for 70 days after the last study drug administration.

Crohn's Disease Activity Index (CDAI) will be obtained during the Screening Period and at Weeks 0, 2, 4, 6, 8, 12, 16, 20, and 26/Premature Discontinuation. If the subject doses onsite then the CDAI will also be completed at Weeks 10, 14, 18, 22, and 24. The inflammatory bowel disease questionnaire (IDBQ) will be administered at Weeks 0, 4, 8, and 26/PD.

Subjects should adhere to the required visit schedule. Study visits should occur within the ± 3 day visit window. The Baseline visit at Week 0 should occur within 35 days of the Screening visit.

Diagnosis and Main Criteria for Inclusion/Exclusion:

Main Inclusion:

1. Male or female of Chinese descent with full Chinese parentage 18 to 70 years (inclusive) of age at Baseline (Week 0).
2. Confirmed diagnosis of Crohn's disease for at least 3 months prior to Baseline (Week 0). Appropriate documentation of biopsy results consistent with the diagnosis of CD, in the assessment of the Investigator, must be available.
3. Subject has hs-CRP ≥ 3 mg/L in all laboratory measurements during the Screening Period.
4. Crohn's Disease Activity Index (CDAI) ≥ 220 and ≤ 450 at Baseline (Week 0) despite concurrent or prior treatment with an adequate course, in the opinion of the investigator, of at least one of the following (oral corticosteroids or immunosuppressants or both as defined below):
 - Subjects taking oral corticosteroids, excluding budesonide:
 - Oral corticosteroid dose must be ≤ 20 mg/day (prednisone or equivalent);
 - For subjects with a dose > 10 and ≤ 20 mg/day, dose has been stable for at least 7 days prior to Baseline and the duration of the current steroid course has been at least 14 days prior to Baseline.
 - For subjects with a dose ≤ 10 mg/day, dose has been stable for at least 10 days prior to Baseline (Week 0) and the duration of the current steroid course has been at least 14 days prior to Baseline (Week 0).
 - Subjects taking oral budesonide:
 - Dose must not exceed 9 mg/day;

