5.2 Variables Used for Stratification of Randomization

At Baseline (Week 0), subjects were randomized in a 1:1 ratio to receive adalimumab or placebo. The randomization was stratified by Crohn's disease severity (CDAI \leq 300, $>$ 300) at Baseline (Week 0) and corticosteroid use at Baseline.

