10.0 Efficacy Analysis

10.1 General Considerations

All statistical tests will be two-sided with the significance level of 0.05. Descriptive statistics will be provided. These include the number of observations, mean, standard deviation, minimum, median, and maximum for continuous variables; and number and percent for discrete variables. The analysis will be performed using SAS® (SAS Institute Inc., Cary, NC, USA).

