10.3 Secondary Efficacy Analyses

The Week 26 efficacy endpoint is proportion of subjects who achieve clinical remission at Week 26 (CDAI < 150) in subjects who achieved clinical response (decrease in CDAI ≥ 70 points from Baseline) at Week 8. The one sample Exact test will be performed by comparing it to the clinically meaningful remission rate of 30%, and the two-sided 95% CI will be provided.

Key secondary efficacy endpoints include:

- Proportion of subjects who achieve CDAI < 150 plus a reduction in hs-CRP of at least 50% from Baseline at Week 4.
- Proportion of subjects who achieve CDAI < 150 plus a reduction in hs-CRP of at least 50% from Baseline at Week 26 in subjects who achieved decrease in

CDAI \geq 70 points from Baseline plus at least 30% reduction in hs-CRP from Baseline at Week 8.

- Proportion of subjects who discontinue corticosteroid use and achieve clinical remission (CDAI $<$ 150) at Week 26 in subjects who were taking steroids at Baseline and who achieved clinical response (decrease in CDAI \geq 70 points from Baseline) at Week 8.
- Proportion of subjects who discontinue corticosteroid use and achieve CDAI $<$ 150 plus a reduction in hs-CRP of at least 50% from Baseline at Week 26 in subjects who were taking steroids at Baseline and who achieved decrease in CDAI \geq 70 points from Baseline plus a reduction in hs-CRP of at least 30% from Baseline at Week 8.
- Proportion of subjects who achieve clinical response (decrease in CDAI \geq 70 points from Baseline) at Week 4.
- Proportion of subjects who achieve decrease in CDAI \geq 70 points from Baseline plus a reduction in hs-CRP of at least 30% from Baseline at Week 4.
- Proportion of subjects who achieve CDAI $<$ 150 and hs-CRP $<$ 3 mg/L at Week 4.
- Proportion of subjects who achieve CDAI $<$ 150, hs-CRP $<$ 3 mg/L at Week 26 in subjects who achieved clinical response (decrease in CDAI \geq 70 points from Baseline) at Week 8.
- Proportion of subjects who achieve IBDQ remission (IBDQ \geq 170 points) at Week 4.
- Proportion of subjects who achieve IBDQ remission at Week 26 in subjects with clinical response (decrease in CDAI \geq 70 points from Baseline) at Week 8.
- Change from Baseline in fecal calprotectin level at Week 4.
- Proportion of subjects who achieve CDAI $<$ 150, hs-CRP $<$ 3 mg/L and fecal calprotectin $<$ 250 μ g/g at Week 4.

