- Proportion of subjects who achieve CDAI $<$ 150, hs-CRP $<$ 3 mg/L and fecal calprotectin $<$ 250 μ g/g at Week 26 in subjects who achieved clinical response (decrease in CDAI \geq 70 points from Baseline) at Week 8.

Additional secondary endpoints include:

- Proportion of subjects with clinical remission (CDAI < 150) over time.
- Proportion of subjects with CDAI < 150 plus a reduction in hs-CRP of at least 50% from Baseline over time.
- Proportion of subjects with clinical response (decrease in CDAI \geq 70 points from Baseline) over time.
- Proportion of subjects with decrease in CDAI \geq 70 points from Baseline plus a reduction in hs-CRP of at least 30% from Baseline over time.
- Change from Baseline in CDAI over time.
- Change from Baseline in hs-CRP level over time.
- Change from Baseline in fecal calprotectin level over time.

The analysis over time will be performed for the DB placebo-controlled period (Week 0 to Week 4), with comparisons between active treatment and placebo groups. The analysis over time will also be performed for Any Adalimumab set (the entire study on or after the first dose of adalimumab), with only summary statistics for adalimumab treatment.

Exploratory endpoints include:

- Proportions of subjects who achieve CDAI < 150 at Week 26 in subjects who did not achieve clinical response (decrease in CDAI \geq 70 points from Baseline) at Week 8.

For categorical endpoints with comparison between the treatment groups, the difference in proportions of subjects between treatment groups will be analyzed using the CMH test adjusted for stratification variables. Additionally, the CMH based two-sided 95% confidence interval for the difference in proportions will be provided. For categorical endpoints with comparison to the clinically meaningful constant rate, the one sample Exact test will be performed and the two-sided 95% CI will be provided. The NRI imputation method will be used for subjects with missing data at the time point

evaluated. Subjects who dose-escalate will be imputed using NRI for visits after dose escalation. The LOCF method will also be used as the sensitivity analyses.

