Change from Baseline in continuous endpoints will be analyzed using Analysis of Covariance (ANCOVA) model including factor for treatment group, stratification factors and Baseline values. For analyses of changes from Baseline variables, both LOCF and observed case analyses will be performed. The LOCF analysis is considered primary for inferential purposes.

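### Week 4 IBDQ remission is compared without the baseline IBDQ score already collected: a valid analysis that probably gives up some precision

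*SAP*

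**What the plan says.** SAP 10.3 lists "Proportion of subjects who achieve IBDQ remission" at Week 4, with a threshold of 170 points, among 13 key secondary endpoints. For binary endpoints compared between arms, "the difference in proportions of subjects between treatment groups will be analyzed using the CMH test adjusted for stratification variables", with a CMH-based 95% CI for the risk difference. SAP 5.2 names the variables: "The randomization was stratified by Crohn's disease severity" (CDAI ≤ 300, > 300) and by baseline corticosteroid use. Protocol 8.1.4.2 plans the same test.

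The Protocol synopsis says that the questionnaire "will be administered at Weeks 0, 4, 8, and 26/PD", so a baseline score exists. SAP 7.1 uses that score only as a baseline characteristic, summarised and compared between arms. No efficacy model, stratum, subgroup (SAP 10.5) or sensitivity analysis includes it; the LOCF analysis changes only the imputation.

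For change-from-baseline endpoints, by contrast, SAP 10.3 specifies an ANCOVA "model including factor for treatment group, stratification factors and Baseline values". No IBDQ change-from-baseline analysis is planned.

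**The concern.** IBDQ remission is an absolute threshold, so where a subject starts should help predict whether he or she reaches 170 four weeks later. Entry requires CDAI ≥ 220, so nobody eligible starts in CDAI remission. No entry criterion limits baseline IBDQ, and a subject could enter near or above 170. The two-level CDAI stratum is only a coarse stand-in for that starting position.

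Improved quality of life is a stated additional objective. Week 4 IBDQ remission is its only randomised comparison, because the other IBDQ endpoint is at Week 26 in Week 8 responders, when everyone receives adalimumab. At stake is a wider interval, and a lower chance of showing a real difference, than data already in hand would allow. SAP 7.1 puts a p-value on baseline IBDQ but specifies no response to an imbalance, so any adjustment added after unblinding would be post hoc.

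**Working it through.** **Inputs from the documents.** 200 subjects, 1:1 (SAP 4.2, 4.3); four strata (SAP 5.2); two-sided 0.05 (SAP 10.1); Week 4 planning rates of 24% vs 47%, which are for CDAI remission (SAP 4.3).

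**Assumptions, not in the documents.** Correlation ρ between baseline and Week 4 IBDQ of 0 to 0.7; correlation of baseline IBDQ with CDAI of 0.4 (0.2 and 0.6 also tried); half of subjects with CDAI > 300; 40% on steroids, with steroid use not prognostic; no missing outcomes; IBDQ remission rates of 24% vs 47% (borrowed from the primary endpoint) or 20% vs 35%.

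**Step 1: the plan's own figure.** Summing the two binomial probabilities over all tables (100 per arm, 24% vs 47%) in which two-sided Fisher p ≤ 0.05 gives 90.7%. The stated 90% reproduces. It belongs to CDAI remission; no power is stated for IBDQ remission.

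**Step 2: model.** Latent Week 4 score = ρB + √(1 − ρ²)·ε + δT, where B is standardised baseline IBDQ and T is treatment. Remission means a score above c = Φ⁻¹(1 − p₀), with δ = c − Φ⁻¹(1 − p₁).
- 24% vs 47%: c = 0.706, δ = 0.706 − 0.075 = 0.631.
- 20% vs 35%: c = 0.842, δ = 0.842 − 0.385 = 0.456 (unrounded inputs).

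Allocation is 1:1 within strata, with 4,000 simulated trials per row.

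**Step 3: the two analyses.**
- CMH risk difference = Σwₛ(p̂₁ₛ − p̂₀ₛ)/Σwₛ, with wₛ = n₁ₛn₀ₛ/nₛ, and the CMH test.
- Adjusted: logistic regression on strata, B and T; average over all subjects of predicted risk if treated minus predicted risk if not; likelihood-ratio test.
- Ratio = Var(CMH)/Var(adjusted). Variance cut = 1 − 1/ratio.

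| Rates | ρ | SE, CMH | SE, adjusted | Ratio | Cut | Power, CMH → adjusted |
|---|---|---|---|---|---|---|
| 24 vs 47% | 0 | 0.0661 | 0.0664 | 0.993 | −0.7% | 92.6 → 93.0% |
| | 0.3 | 0.0668 | 0.0649 | 1.061 | 5.7% | 92.8 → 94.5% |
| | 0.5 | 0.0657 | 0.0612 | 1.150 | 13.0% | 93.4 → 96.4% |
| | 0.7 | 0.0638 | 0.0548 | 1.359 | 26.4% | 93.9 → 98.5% |
| 20 vs 35% | 0 | 0.0620 | 0.0621 | 0.996 | −0.4% | 66.2 → 67.2% |
| | 0.3 | 0.0624 | 0.0609 | 1.050 | 4.8% | 66.4 → 69.4% |
| | 0.5 | 0.0618 | 0.0579 | 1.139 | 12.2% | 67.4 → 74.7% |
| | 0.7 | 0.0616 | 0.0530 | 1.354 | 26.1% | 67.3 → 82.0% |

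The mean risk differences of the two methods agree to within about 0.001 in every row, so adjustment does not change what is estimated. A separate simulation of 200 subjects gave cuts of about 4% at ρ = 0.3, 9–15% at 0.5 and 24–27% at 0.7. Together the ranges are 4–6%, 9–15% and 24–27%.

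**Step 4: does the CDAI stratum recover the loss?** At ρ = 0.5 and 24% vs 47%, IBDQ–CDAI correlations of 0.2 and 0.6 give ratios of 1.151 and 1.166. It does not.

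**Step 5: test size.** With no treatment effect and ρ = 0.5, rejection rates are 5.4% (CMH) and 5.8% (likelihood ratio), with Monte Carlo SE √(0.05 × 0.95/4,000) = 0.34 points. At ρ = 0 the likelihood-ratio test shows 0.4 and 1.0 points more power, which is test size and not precision. Net of that, the smallest gains fall from 1.7 to 1.3 points (24% vs 47%) and from 3.0 to 2.0 points (20% vs 35%). The variance ratios are unaffected.

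**The case against.** CMH on the randomisation strata is valid, pre-specified and light on assumptions. It matches the primary method and already yields a risk difference with an interval. Every figure for the size of the loss depends on inputs from outside the documents. If the IBDQ effect is as large as that planned for CDAI remission, CMH power is already 93–94%. Eligibility confines CDAI to 220–450, which may also narrow the spread of baseline IBDQ and push towards the low end. Secondary endpoints carry no multiplicity adjustment (SAP 10.4), so no other test depends on this one.

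All of that stands, and it limits the point to efficiency on one key secondary endpoint. It does not remove the point: the score is collected, the same SAP section already adjusts continuous endpoints for their own baseline, and adjustment loses almost nothing even at zero correlation.

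Four stronger readings are tempting but not supported:
- **That the planned result is biased, or that a chance imbalance would invalidate it.** The CMH interval already allows for chance imbalance under randomisation, and SAP 7.1 would make an imbalance visible.
- **That the variance cut could reach 36%.** A CMH variance 1.36 times the adjusted one is a cut of 1 − 1/1.36 = 26%. Nothing in the documents supports a stronger case than ρ = 0.7.
- **That the Week 4 composite of CDAI < 150 and hs-CRP < 3 mg/L needs the same change for baseline hs-CRP.** The simulated variance gain there is only 1–8%, too little to justify a second bespoke model.
- **That the primary analysis must change too.** Its baseline measure, CDAI, is already in the stratification in two-level form.

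**Conclusion.** The point holds as a matter of efficiency. The plan leaves out of the only randomised quality-of-life comparison a baseline score that it collects. If baseline and Week 4 IBDQ correlate at 0.3 to 0.7, the cost is equivalent to roughly 10 extra subjects (200 × 0.05) to 72 (200 × 0.36). The power gain from adjustment is about 1–5 points if the effect is as large as the primary's and about 3–15 points for a smaller one; a point or less of this is test size. Some positive correlation is to be expected on the same scale four weeks apart, but the documents do not give it. Imputing missing outcomes as non-remission would probably weaken it, and the simulation did not include that. The direction is therefore secure and the size is not. The primary conclusion is unaffected.

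**What to change.** Before unblinding, specify in SAP 10.3 for Week 4 IBDQ remission:
- a logistic model with treatment, the two stratification factors and continuous baseline IBDQ;
- the standardised risk difference as the main result, with a 95% CI and test from one named variance method (for example the delta method with robust variance, or the bootstrap);
- missing baseline IBDQ replaced by the overall mean, and non-responder imputation kept for the outcome;
- the planned CMH result shown as support.

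Record the departure from Protocol 8.1.4.2 in SAP 12.1. Leave the primary CMH analysis and the hs-CRP composites as planned.

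The cost is SAP wording and one extra model; no new data are needed. The downsides are mild dependence on the model, a different main method from the parallel Week 4 binary endpoints, and possibly a slightly liberal test (about 5–6% in simulation).

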- u. Collection of Serious Adverse Events (SAEs) and protocol-related nonserious adverse events begins the day the subject signs the informed consent. Collection of AEs begins on Day -7 for subjects who initiate TB prophylaxis.
- v. Administration of drug should be performed after all assessments and examinations scheduled for that day have been completed as much as possible. Starting at or after Week 12 and if the subject qualifies for dose escalation (criteria defined in Section 5.3.1.1 and per investigator discretion), the subject may receive 80 mg of adalimumab eow.
- w. Dosing may occur onsite by appropriate site staff or the subject or their qualified designee can administer doses when not at the site.
- x. For damaged or replacement study drug, subject should stay on their dosing schedule established by the Baseline (Week 0) visit.
- y. Procedure should be performed if subject doses onsite, if subject doses at home these procedures are not required.

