Study drug will be administered to all subjects onsite by site medical staff during all the visits from Baseline (Week 0) through Week 24. No study drug will be administered at Week 26. Detailed instructions and training for the administration of adalimumab are provided in [Appendix E](#) and [Appendix F](#). Study drug kits are assigned by IRT following the subjects randomized treatment schedule. If the subject chooses to dose outside of the clinic at the visit weeks specified in [Table 1](#), adalimumab injections occurring during study visits will be performed at the visit by the subject or their designated family member, friend or Healthcare Professional under the supervision of trained medical personnel to reinforce proper aseptic SC injection technique. Subjects or a trained designated family member, friend or Healthcare Professional will perform the injections of adalimumab in the subject's home during the weeks they are not in for scheduled clinic visits.

When dosing onsite, each subject will have a Dosing Log or accountability form at Baseline (Week 0); this log must be filled out each time a dose is administered. In the dosing log, the date and time study drug is administered, and the dose administered will be recorded. Additionally, any discernible departure from the protocol regarding study

drug administration will be recorded on the source documents and on the appropriate drug accountability form.

Site medical staff or subjects, if dosing occurs at the subject's home, should administer study medication on the same day of the week. The dosing dates for all doses of study drug should be calculated from the Baseline (Week 0) Visit date. A ± 3 -day window is allowable for scheduled study dosing dates. For subjects who deviate from this dosing window, every effort should be made to bring the subject back to the original dosing schedule as soon as possible. For situations where bringing the subject back on the original dosing schedule will cause the dose to be out of the ± 3 day window, please contact the AbbVie SDP for additional instructions.

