Appendix F. Sample Injection Instructions for at Home Dosing – Pre-Filled Syringe

Subject Instructions

0.8 mL dose

(Administered as a single dose-pre-filled syringe)

Protocol M14-233

Tables of Contents:

Dosing Schedule

General Information and Supplies

Injection Procedures

Study Drug Dosing Schedule

Subject Number: _____

You will require subcutaneous injections throughout the study.

You will receive the following number of injections during the study:

- Baseline Visit (the first visit to receive study medication for this study), you will receive 4 injections (2 kits) at the clinic.
- Week 2 you will receive 2 injections (1 kit) at the clinic.
- At Week 4 you will receive 4 injections at the clinic.
- At Week 6 you will receive 2 injections at the clinic.
- At Week 8 you will receive 1 injection at the clinic.
- Week 10 you will administer 1 injection at home.
- At Weeks 12, 16, and 20 you will receive 1 injection at the clinic if you have not dose escalated. If you have dose escalated then you will receive 2 injections at the clinic.
- At Weeks 14, 18, 22, and 24 you will administer 1 injection at home if you have not dose escalated. If you have dose escalated then you will administer 2 injections at home.

For all doses, kits must be used in the order dispensed. All doses of study medication must be taken in order, starting with the syringe labeled with a "1," then at the next dose, using the syringe labeled with a "2."

Please return all used and unused syringes and empty boxes to the clinic on your next visit. Used syringes should be placed in the special sharps container provided. All unused syringes should be returned in the original box.

If an injection is missed or something occurs where the full dose cannot be injected, contact your study center immediately for further instructions. Please record any missed doses on your subject dosing diary.

Remember to complete your dosing diary after each injection and to call the doctor's office if you are having problems administering your study medication.

General Information

- Pre-filled syringes will be labeled "Adalimumab" versus Placebo.
- Store all adalimumab pre-filled syringes in your refrigerator NOT in the freezer. Should the syringes accidentally become frozen, call your study doctor's office.
- Study medication should be taken at about the same time of day, on the same day of the week as directed by your study doctor.

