v. Administration of drug should be performed after all assessments and examinations scheduled for that day have been completed as much as possible. Starting at or after Week 12 and if the subject qualifies for dose escalation (criteria defined in Section 5.3.1.1 of Protocol Amendment 1 and per investigator discretion), the subject may receive 80 mg of adalimumab eow.

w. Dosing may occur onsite by appropriate site staff or the subject or their qualified designee can administer doses when not at the site.

x. For damaged or replacement study drug, subject should stay on their dosing schedule established by the Baseline (Week 0) visit.

y. Procedure should be performed if subject doses onsite, if subject doses at home these procedures are not required.

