Week 22	155	149 – 162
Week 24	169	163 – 176
Week 26	183	177 – 190

Rx Day B = date of visit – date of first dose of adalimumab + 1

- a. Date of first dose of adalimumab in double-blind treatment period.

Table 7. Visit Windows for Analysis of hs-CRP, Chemistry and Hematology (Any Adalimumab)

Visit Week	Nominal Day	Time Window (Rx Day B Range)
Week 0	1 ^a	≤ 1
Week 2	15	2 – 22
Week 4	29	23 – 36
Week 6	43	37 – 50
Week 8	57	51 – 71
Week 12	85	72 – 99
Week 16	113	100 – 127
Week 20	141	128 – 162
Week 26	183	163 – 190

Rx Day B = date of visit – date of first dose of adalimumab + 1

a. Date of first dose of adalimumab in double-blind treatment period.

Table 8. Visit Windows for Analysis of Urinalysis (Any Adalimumab)

Visit Week	Nominal Day	Time Window (Rx Day B Range)
Week 0	1 ^a	≤ 1
Week 4	29	2 – 43
Week 8	57	44 – 71
Week 12	85	72 – 112
Week 20	141	113 – 161
Week 26	183	162 – 190

Rx Day B = date of visit – date of first dose of adalimumab + 1

a. Date of first dose of adalimumab in double-blind treatment period.

Table 9. Visit Windows for Analysis of Fecal Calprotectin and IBDQ (Any Adalimumab)

Visit Week	Nominal Day	Time Window (Rx Day B Range)
Week 0	1 ^a	≤ 1
Week 4	29	2 – 43
Week 8	57	44 – 71
Week 26	183	72 – 190

Rx Day B = date of visit – date of first dose of adalimumab + 1

a. Date of first dose of adalimumab in double-blind treatment period.

Definition of Missing Data Imputation

The following imputation methods will be used to impute missing values in the efficacy analyses. In addition, an observed case analysis will be performed.

Non-Responder Imputation (NRI)

The NRI approach is used for binary efficacy variables. These variables can take values of 'Achieved' or 'Not Achieved' or may be missing for any reason including discontinuation from study. According to the NRI imputation approach, all missing value will be considered as 'Not Achieved.'

Subjects who dose-escalate from OL adalimumab 40 mg eow to OL adalimumab 80 mg eow due to disease flare or non-response will be imputed as 'Not Achieved' in the analysis of binary efficacy variables.

For the analysis of Week 26 efficacy variables only for dose-escalated subjects, the remission/response status will be determined based on the observed data at Week 26 after the dose escalation.

Last Observation Carried Forward (LOCF)

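### Read literally, the SAP's non-responder rule scores subjects as failures at open-label weeks where the protocol required no CDAI of them, which distorts the descriptive remission and response displays over time

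*SAP*

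**What the plan says.** **Collection.** The protocol synopsis states: "If the subject doses onsite then the CDAI will also be completed at Weeks 10, 14, 18, 22, and 24". Note y to the study activities table, in both documents, adds that "if subject doses at home these procedures are not required". Note w to the same table permits dosing away from the site, and the home-dosing instructions in protocol Appendix F tell the subject: "At Weeks 14, 18, 22, and 24 you will administer 1 injection at home if you have not dose escalated". The same list gives Week 10 as a home injection.

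**Conflicting text.** Protocol 5.3.1.1 (Study Drug Dispensing/Administration) opens with: "Study drug will be administered to all subjects onsite by site medical staff during all the visits from Baseline (Week 0) through Week 24". Later in that paragraph it provides for injections at home.

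**Analysis.** SAP 10.3 lists as an additional secondary endpoint: "Proportion of subjects with clinical remission (CDAI < 150) over time". Clinical response over time is listed with it. Both are to be summarised on the Any Adalimumab set from the first adalimumab dose to the end of the study. SAP Table 6 gives CDAI its own windows at Weeks 10, 14, 18, 22 and 24, counted from the first adalimumab dose.

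**Missing data.** SAP 10.3 says: "The NRI imputation method will be used for subjects with missing data at the time point" evaluated. SAP 6.0 defines NRI for values missing for any reason, so that "all missing value will be considered as 'Not Achieved". Neither section exempts a value that is missing because the protocol did not ask for it. LOCF (as sensitivity) and observed-case analyses are also planned.

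**The concern.** NRI is a conservative convention for subjects who drop out or whose outcome is unknown at a visit they should have attended. Here it would also reach subjects who followed the protocol exactly. A home-dosing subject in remission at study Weeks 8, 12, 16, 20 and 26 would be shown as out of remission at Weeks 10, 14, 18, 22 and 24, solely because no score was requested.

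The displays are meant to show how remission and response hold up during open-label treatment. If a material share of subjects dose at home, the curve may dip and recover with the place of dosing and not with the disease, and a reader could take the dips for loss of response.

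**Working it through.** The plan gives no figure on this point, so there is none to reproduce. The check has three steps.

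**1. Can a mandatory visit fill an optional window?** Study Week w is nominally Day 7w + 1, with ±3 days allowed. Windows are from SAP Table 2.

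| Mandatory visit | Days | Own window |
|---|---|---|
| Week 8 | 54–60 | 51–64 |
| Week 12 | 82–88 | 79–92 |
| Week 16 | 110–116 | 107–120 |
| Week 20 | 138–144 | 135–148 |
| Week 26 | 180–186 | 177–190 |

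Each stays inside its own window. The windows for Weeks 10 (65–78), 14 (93–106), 18 (121–134), 22 (149–162) and 24 (163–176) can be filled only by an on-site dosing visit or an unscheduled assessment.

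**2. Where do these visits fall on the Any Adalimumab scale?** Table 6 counts from first adalimumab. For the adalimumab-first arm, the weeks are unchanged. For the placebo-first arm, first adalimumab is at study Week 4 (Day 29), so the day count is the study day − 29 + 1 = study day − 28, a shift of four weeks:

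- Optional study Weeks 10, 14, 18, 22 and 24 become analysis Weeks 6, 10, 14, 18 and 20.
- Study Week 26 becomes Day 183 − 28 = 155, inside the Week 22 window (149–162). With ±3 days on both the visit and the first adalimumab dose, it ranges from Day 149 to 161 and stays there.
- Nothing is scheduled for this arm in the analysis Week 24 (163–176) or Week 26 (177–190) windows.

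Only analysis Weeks 2, 4, 8, 12 and 16 therefore have a CDAI required of both arms.

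**3. What rate would be displayed?** Let p be the true rate and h the share dosing at home. Neither is given for these visits, so p = 50% and the values of h are assumptions. Assume also equal arms, no dropout or dose escalation, and home dosing unrelated to outcome.

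| Analysis week | Required CDAI | Displayed rate | h = 0 | h = 30% | h = 50% | h = 80% |
|---|---|---|---|---|---|---|
| 2, 4, 8, 12, 16 | both arms | p | 50% | 50% | 50% | 50% |
| 6, 20, 22 | one arm; optional in the other | p(1 − h/2) | 50% | 42.5% | 37.5% | 30% |
| 10, 14, 18 | neither; optional in both | p(1 − h) | 50% | 35% | 25% | 10% |
| 24 | none; optional in one arm, no visit in the other | p(1 − h)/2 | 25% | 17.5% | 12.5% | 5% |
| 26 | one arm; no visit in the other | p/2 | 25% | 25% | 25% | 25% |

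For example, at h = 50% and Week 10: 0.50 × (1 − 0.50) = 25%. The Week 26 row does not depend on h. The placebo-first arm has left the study by then, and literal NRI halves the pooled rate even if nobody doses at home.

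**The case against.** **Reach.** After Week 4 the over-time analysis consists of summary statistics, with no comparison and no test. Only remission and response are at issue at the optional study weeks. The two composites also need hs-CRP, which is not scheduled at those weeks for anyone. This stands, and it limits the weight of the point.

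**The link is inferred.** The SAP never lists the visits for the over-time displays. The NRI sentence in 10.3 sits among endpoints compared between groups or with a constant, and the window tables also serve vital signs and are built so that no measurement is discarded. This is fair, but the general rule in SAP 6.0 covers binary efficacy variables without exception and Table 6 names CDAI. The literal reading is the natural one, and nothing in the SAP prevents it.

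**Other analyses are planned.** LOCF would carry the last mandatory result forward (study Week 8 to 10, 12 to 14, 16 to 18, 20 to 22 and 24), so the subject described above would stay in remission. Set beside LOCF and observed case, the dips would look like an imputation effect. This partly stands. LOCF is only the sensitivity analysis, and observed case at the optional weeks uses subjects who chose to attend.

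**Size.** The home-dosing share is unknown, and one protocol sentence has all dosing on site through Week 24. If on-site dosing predominates, the effect at the optional visits is near zero. This stands, which is why only a range can be given. It does not remove the gap at analysis Weeks 24 and 26.

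**Dose escalation.** A reader might infer that escalating between mandatory visits always requires a new on-site CDAI, so that on-site attenders must be the sicker subjects. Protocol 5.3.1.1 (Dose Escalation) does not support this. The latest hs-CRP is first paired with the previous visit's CDAI, so a subject can qualify on a mandatory score. Attendance is self-selected, but the documents do not fix the direction of the selection.

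**Conclusion.** The point holds for the descriptive remission and response displays on the Any Adalimumab set. Applied as written, NRI gives a wrong displayed rate at visits where the protocol required no CDAI. An assumed true 50% shows as 35%, 25% or 10% at home-dosing shares of 30%, 50% or 80% where the visit is optional in both arms. At analysis Week 26 it shows as 25% whatever that share. These sizes rest on the assumptions in the table above and on reading the general NRI rule as covering every Table 6 window.

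Two stronger readings are not supported. One is that the curve will certainly rise and fall: that depends on a home-dosing share the documents do not give. The other is that the main conclusions are compromised: the Week 4 primary endpoint, Week 8 response and the study Week 26 endpoints use visits where CDAI is required of every subject.

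**What to change.** In SAP 10.3, state that NRI is not applied where the protocol required no CDAI of the subject. Then choose one of these:

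- **Pooled Any Adalimumab display:** apply NRI to CDAI remission and response only at analysis Weeks 2, 4, 8, 12 and 16.
- **Display by randomised arm on study weeks:** limit NRI to the mandatory visits (Weeks 2, 4, 6, 8, 12, 16, 20 and 26).

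The study-week list must not be carried into the pooled display. There it would still fail placebo-first home dosers at analysis Weeks 6 and 20, and every placebo-first subject at Week 26.

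Show the other weeks as observed data with the number assessed, and note that on-site attendance is self-selected. In the protocol, reconcile the statement in 5.3.1.1 that all dosing is on site through Week 24 with Table 1 notes w and y and Appendix F.

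The cost is a few sentences and fewer points on the NRI curve. No required data are lost.
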